### **7.6.7 Immune modulating medication**

See Core Safety SAP

### **7.6.8 Multiple Events**

See Core Safety SAP

### **7.6.9 Clinical laboratory evaluations**

See Core Safety SAP with the exception that scatterplots for total bilirubin will not be produced.

### **7.6.10 Vital Signs, Pulse Oximetry and Medical Procedures**

See Core Safety SAP. A by-subject listing of the medical procedures will be produced.

### **7.6.11 Immunogenicity Analysis**

See Core Safety SAP

### **7.6.12 Pregnancy**

By-subject listing of pregnancy tests results will be provided

### **7.6.13 Clinical Safety Program (CSP)**

See Core Safety SAP

### **7.6.14 Adverse Events by Subgroup**

See Core Safety SAP

### **7.6.15 Immune-mediated Adverse Events Analysis**

IMAE analyses will include events, regardless of causality, occurring within 100 days of the last dose. These analyses are limited to subjects who received immunosuppressive medication for treatment of the event, with the exception of endocrine events (hypothyroidism/thyroiditis, hyperthyroidism, hypophysitis, diabetes mellitus, adrenal insufficiency), which will be included in the analysis regardless of treatment since these events are often managed without immunosuppression.

IMAEs, serious IMAEs, IMAEs leading to discontinuation, and IMAEs leading to dose delay or reduction will be summarized by worst CTC grade and presented by IMAE Category/PT.

Time to onset, time to resolution, time to resolution with completion of immunosuppressive medication will be defined and summarized by IMAE category in the same manner as for select AEs (see [Section 7.6.6](#)) except that, other than for the endocrine category, the longest duration of IMAEs has to be associated with the use of an immune-modulating medication. Time to Resolution for Longest Any Grade or Grade 3-5 IMAE cluster per subject will be listed.

Use of immune-modulating medications for IMAE management will be summarized by IMAE category in a similar manner as for the select AEs (see [Section 7.6.7](#)).

IMAE rechallenge will be also summarized.

### **7.6.16 Other Events of Special Interest**

In addition to select AE and immune-mediated AE, categories of other events of special interest (OESI) have been defined (i.e. myasthenic syndrome, Guillain-Barre syndrome, demyelination, pancreatitis, uveitis, encephalitis events). Worst CTC grade of any and drug-related OESI (both safety windows) will be summarized along with the time to onset and resolution. In addition, worst CTC grade of serious OESI and OESI leading to discontinuation will be summarized (both safety

windows). Lastly, OESI occurring within 100 days of the last dose in subjects who received immunosuppressive medication for treatment of the events will be tabulated by worst CTC grade and the time to onset and resolution will be provided.

[REDACTED]

[REDACTED]

[REDACTED]

[REDACTED]

[REDACTED]

still on treatment have completed 8 weeks follow-up (after the first scheduled tumor assessment). If there are 8 or fewer responses in these 37 subjects, the study will be stopped (in both the ASCT-failed and the ASCT ineligible cohorts). Otherwise, approximately 53 additional subjects will be accrued to target a total of 90 treated subjects in the ASCT failed group. Accrual and treatment will continue during the time period that the interim analysis is being conducted. This may result in more than 37 treated subjects in the event that the study is terminated for lack of efficacy. The tolerability of the regimen will continue to be evaluated by the sponsor with the investigators to ensure that it is acceptable for continued enrollment.

The following analyses will be performed at interim analysis on the first 37 ASCT-failed cohort treated subjects.

- Pre-Treatment Subject Status Summary
- End of treatment period subject status summary
- Demographic characteristics summary
- Baseline Physical Measurements summary
- Other baseline characteristics summary
- Prior cancer therapy summary
- Cumulative dose and relative dose intensity summary
- Best overall response, per IRRC
- Time to response and duration of response, per IRRC
- Event Chart for Tumor Response, Tumor Progression, Duration of Therapy and Death
- Waterfall plot of best reduction in Target Lesion, per IRRC
- Spider plot of Tumor Burden Change, per IRRC
- Best overall response, per investigator
- Kaplan Meier plot of PFS, per IRRC
- Kaplan Meier plot of overall survival
- Status of Censored Subjects, OS Analysis
- Subsequent cancer therapy summary
- Death summary
- Summary of any adverse events by worst CTC grade (any grade, grade 3-4, grade 5), 5% cutoff, 30 days safety window
- Summary of Drug-Related Adverse Events by Worst CTC Grade (Any Grade, Grade 3-4, Grade 5), no cutoff, 30 days safety window
- Summary of Serious Adverse Events by Worst CTC Grade (Grade 1, Grade 2, Grade 3, Grade 4, Grade 5, unknown grade, any grade), no cutoff, 30 days safety window
- Summary of Drug-Related Serious Adverse Events by Worst CTC Grade (Any Grade, Grade 3-4, Grade 5), no cutoff, 30 days safety window

- Summary of Adverse Events Leading to Discontinuation by Worst CTC Grade (Grade 1, Grade 2, Grade 3, Grade 4, Grade 5, unknown grade, any grade), no cutoff, 30 days safety window
- Summary of Any Select Adverse Events by Worst CTC Grade (Any Grade Grade 3-4 Grade 5), no cutoff, 30 days safety window
- Summary of Drug-Related Select Adverse Events by Worst CTC Grade (Any Grade, Grade 3-4, Grade 5), no cutoff, 30 days safety window

In addition, the following analyses will be also performed at interim analysis.

- Demographic characteristics summary (ASCT Ineligible cohort and pooled with ASCT-Failed 37 subjects)
- Best overall response, per investigator (ASCT Ineligible cohort)
- Summary of Tumor Specimen Acquisition and Characteristics for PD-L1 (ASCT-Failed 37 subjects and ASCT Ineligible cohort pooled)
- Best Overall Response and Objective Response per Investigator for each PD-L1 Expression Status Group (ASCT-Failed 37 subjects, ASCT Ineligible and pooled)
- Box Plot of PD-L1 Expression versus Response Status (ASCT-Failed 37 subjects and ASCT Ineligible cohort pooled)
- Kaplan-Meier Plot of Overall Survival by PD-L1 Status at Baseline  
Kaplan-Meier Plot of Progression Free Survival per investigator by PD-L1 Status at Baseline (ASCT-Failed 37 subjects and ASCT Ineligible cohort pooled)
- Kaplan-Meier Plot of Progression Free Survival per investigator by PD-L1 Status at Baseline (ASCT-Failed 37 subjects and ASCT Ineligible cohort pooled)
- Best Overall Response and Objective Response per Investigator for each Cell of Origin Subtype (ASCT-Failed 37 subjects and ASCT Ineligible cohort pooled)
- Best Overall Response and Objective Response per Investigator by Double-Hit Status (ASCT-Failed 37 subjects and ASCT Ineligible cohort pooled)
- Best Overall Response and Objective Response per Investigator by Epstein-Barr virus (EBV) Status (ASCT-Failed 37 subjects and ASCT Ineligible cohort pooled)

## 8 CONVENTIONS

The following conventions may be used for imputing partial dates for analyses requiring dates:

For missing and partial adverse event onset dates, imputation will be performed using the Adverse Event Domain Requirements Specification. Missing and partial Non-Study Medication Domain dates will be imputed using the derivation algorithm described in BMS Non-Study Medication Domain Requirements Specification.

For death dates, the following conventions will be used for imputing partial dates:

- If only the day of the month is missing, the 1st of the month will be used to replace the missing day. The imputed date will be compared to the last known alive date and the maximum will be considered as the death date.
- If the month or the year is missing, the death date will be imputed as the last known alive date
- If the date is completely missing but the reason for death is present the death date will be imputed as the last known alive date

For date of progression, the following conventions will be used for imputing partial dates:

- If only the day of the month is missing, the 1st of the month will be used to replace the missing day.
- If the day and month are missing or a date is completely missing, it will be considered as missing.
- In case, the date of death is present and complete, the imputed progression date will be compared to the date of death. The minimum of the imputed progression date and date of death will be considered as the date of progression.

For other partial/missing dates, the following conventions will be used:

- If only the day of the month is missing, the 15th of the month will be used to replace the missing day.
- If both the day and the month are missing, “July 1” will be used to replace the missing information.
- If a date is completely missing, it will be considered as missing.

The following conversion factors will be used to convert days to months or years: 1 month = 30.4375 days and 1 year = 365.25 days.

Duration (e.g. time from first diagnosis to first dosing date, duration response, and time to response) will be calculated as follows:

$$\text{Duration} = (\text{Last date} - \text{first date} + 1)$$

All statistical analyses will be carried out using SAS (Statistical Analysis System software, SAS Institute, North Carolina, USA) unless otherwise noted.

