## 4.2 Secondary Endpoints

### 4.2.1 Duration of Response (IRRC-assessed)

Duration of response (DOR) is defined as the time from first response (CR or PR) to the date of initial objectively documented progression as determined using the 2007 revised International

Working Group Criteria for Malignant Lymphoma or death due to any cause, whichever occurs first. For subjects who neither progress nor die, the DOR will be censored on the date of their last evaluable tumor assessment. Subjects who start subsequent therapy without a prior reported progression will be censored at the last evaluable tumor assessments prior to initiation of the subsequent anticancer therapy. Stem Cell Transplant will be considered as subsequent therapy. This endpoint will only be evaluated in subjects with objective response of CR or PR.

Duration of Stable Disease will also be evaluated for subjects with SD as best response. Duration of SD is defined as the time between the first dose date to the date of the first documented progression, as determined by IRRC, or death due to any cause, whichever occurs first. Subjects who neither progress nor die will be censored at the same time they will be censored for the DOR analysis.

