#### **4.2.2 Complete Remission Rate and Duration (IRRC-assessed)**

The complete remission rate (CRR) is defined as the number of subjects with a BOR of CR according to the 2007 revised International Working Group Criteria for Malignant Lymphoma, based on IRRC assessment, divided by the number of treated subjects.

To further characterize CRR, the duration of CR will also be evaluated in subjects with objective response of CR. Duration of CR is defined as the time from first documentation of CR (the date of first negative FDG-PET scan or the date of first documentation of no disease involvement in the bone marrow (if required), whichever occurs later) to the date of initial objectively documented progression as determined using the 2007 IWG criteria or death due to any cause, whichever occurs first. Censoring will be applied as per DOR definition.

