#### **4.2.4 Progression Free Survival (IRRC-assessed)**

Progression free survival (PFS) is defined as the time from first dosing date to the date of the first documented progression, as determined by an IRRC according to the 2007 revised International Working Group Criteria for Malignant Lymphoma, or death due to any cause, whichever occurs first.

- Subjects who die without a reported progression will be considered to have progressed on the date of their death.
- Subjects who did not progress or die will be considered as not progressed and will be censored on the date of their last assessment.

- Subjects who did not have any on study assessments and did not die will be censored on the first dosing date.
- Subjects who started any subsequent anti-cancer therapy without a prior reported progression will be censored at the last assessment prior to initiation of the subsequent anti-cancer therapy. Stem Cell Transplant will be considered as subsequent therapy.

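### The rule for a progression date with a missing day has a cap but no floor, so an off-schedule progression can be dated before the first dose, first response or last clean assessment

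*SAP*

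**What the plan says.** SAP section 8 opens permissively: "The following conventions may be used for imputing partial dates for analyses requiring dates". It then gives separate rules for death and progression dates.

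- **Death dates.** "If only the day of the month is missing, the 1st of the month will be used to replace the missing day". A lower limit follows: "The imputed date will be compared to the last known alive date and the maximum will be considered as the death date".
- **Progression dates.** The same first-of-month sentence is repeated. The only further comparison is an upper limit, used when the date of death is complete: "The minimum of the imputed progression date and date of death will be considered as the date of progression".

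The same section gives the duration formula. "Duration (e.g. time from first diagnosis to first dosing date, duration response, and time to response) will be calculated as follows": last date minus first date plus 1, with no truncation.

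The starting points are set in SAP section 4.2. For PFS (4.2.4): "Progression free survival (PFS) is defined as the time from first dosing date to the date of the first documented progression". For DOR (4.2.1): "Duration of response (DOR) is defined as the time from first response (CR or PR) to the date of initial objectively documented progression". Duration of CR (4.2.2) starts at the later of the first negative PET and, where required, the first clear marrow. SAP Table 4.2.4-1 counts as events progressions documented between scheduled visits.

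**The concern.** The first-of-month sentence alone is not the problem, since in the death rule a floor follows it. In the progression rule nothing compares the imputed date with the first dose, the first response or the last assessment at which the subject had not progressed. None of SAP 4.1, 4.2.1 to 4.2.4, Table 4.2.4-1 or the visible parts of 7.5 supplies that comparison, and neither does protocol 8.3.

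Applied as written, the rule can put events in an impossible order. A progression dated before first dose gives a PFS of zero or less, and one dated before first response does the same to DOR. One dated before a clean scan contradicts that scan even if the duration stays positive. A Kaplan-Meier analysis has no place for a time of zero or less, so someone would have to decide after seeing the data whether to drop, truncate or re-date the subject.

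**Working it through.** The plan states no figure to reproduce here, so the check is calendar arithmetic on the stated rule.

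**1. Size of the shift.** Progression on day d of a month is moved back d − 1 days, so the range is 0 to 30. Over a 365-day year the total is 7 × 465 (31-day months) + 4 × 435 (30-day months) + 378 (February) = 5,373. The mean is 5,373 / 365 = 14.7 days. The shift is zero only when progression was on the 1st.

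**2. When the order reverses.** Call the first dose, first response or last clean assessment the anchor, and let true progression fall g days after it. The imputed date is strictly before the anchor when d − 1 > g. The table assumes that the day is missing and that progression is spread evenly over the calendar.

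| g (days after anchor) | Probability imputed date precedes anchor |
|---|---|
| 7 | 0.74 |
| 14 | 0.51 |
| 21 | 0.28 |
| 28 | 0.05 |
| 30 or more | 0 |

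For g = 14, for example, d must be at least 16: (7 × 16 + 4 × 15 + 13) / 365 = 185 / 365 = 0.51.

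**3. Can scheduled scans trigger it?** The schedule and windows are in protocol Table 5.4.1-1 and SAP Table 2.1-1.

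- First dose to earliest in-window first scan: (9 − 1 − 1) × 7 = 49 days.
- 8-weekly period, e.g. week 9 to 17: [(17 − 1) − (9 + 1)] × 7 = 42 days.
- Week 33 to 45: [(45 − 2) − (33 + 1)] × 7 = 63 days.
- 12-weekly period, e.g. week 45 to 57: [(57 − 2) − (45 + 2)] × 7 = 56 days.
- Week 93 to 119: [(119 − 3) − (93 + 2)] × 7 = 147 days.
- 6-monthly period: [(145 − 3) − (119 + 3)] × 7 = 140 days.

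Every gap exceeds 30 days. A progression found at an in-window scheduled scan is never dated before the previous scheduled scan or the first dose. The reversal needs an unscheduled or out-of-window assessment. Duration of CR is the exception: its start can be a PET or marrow date off the CT schedule, and that alone can be close enough to the next scheduled scan.

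**4. Examples (dates assumed, day of progression missing).** Section 8 does not name PFS among its examples of durations, so using the + 1 formula for PFS is an assumption. Without it, the PFS figure from the rule would be one day lower.

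| Anchor | True progression | True value | SAP rule |
|---|---|---|---|
| First dose 10 March | 28 March, unscheduled | PFS 19 days | 1 March − 10 March + 1 = −8 |
| First response 6 May | 27 May, unscheduled | DOR 22 days | 1 May − 6 May + 1 = −4 |
| First response 20 March | later in March | DOR 2 to 12 days | 1 March − 20 March + 1 = −18 |

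**The case against.** The best defence is that almost no data can set this off. The primary endpoint and every secondary endpoint except investigator ORR are IRRC-assessed, and central readers work from scans whose dates should be complete. Progression has to be documented by the 2007 criteria: under Table 4.2.4-1, clinical progression without that evidence is censored. A reversal then needs a missing day, an off-schedule assessment and the same calendar month, all together. PFS and DOR are descriptive, earlier dating shortens them and so does not flatter the drug, the conventions are permissive, and a negative duration would be visible in the output. Choosing the 1st of the month is an ordinary convention.

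Most of this stands and sets the size of the point, but it does not remove it. Permissive wording supplies no floor and leaves the remedy to be improvised. Off-schedule progression is foreseen by Table 4.2.4-1. Investigator-assessed dates, which need not pass through central reading, also feed planned analyses: DOR in SAP 4.2.5 and PFS by PD-L1 status in the interim list of SAP 7.10.

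A reader might infer that the primary result is at risk. SAP 4.1 closes the best-response window at progression, so read literally a progression imputed before a subject's only response would remove that response, and 25 of 90 responses rejects the null hypothesis while 24 does not. The documents do not support expecting this. It would take the same coincidence in centrally read data, in a trial sitting exactly on the boundary, and nothing suggests that IRRC dates lack a day.

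**Conclusion.** The gap is real and minor. The progression rule in SAP 8 is bounded only from above, its neighbour for death shows the missing floor, and as written it can give a zero or negative PFS or DOR or a progression dated before a clean assessment. The shift is 0 to 30 days, mean about 15. That measures the effect of any first-of-month rule on a partial date, not how often impossible values arise.

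The frequency cannot be computed, because the documents do not say how often the day is missing. Few subjects are expected, mainly in investigator-assessed analyses, and no stated hypothesis test is expected to change. Two broader readings fail: the rule does not always move the event earlier (it is never later, and is unchanged for the 1st), and scheduled in-window scans are not affected, apart from duration of CR. The conclusion rests on the visible text. Redacted sections could hold a floor, though section 8 refers to none.

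**What to change.** Add to the progression bullets of SAP section 8:

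> If only the day is missing, the progression date will be the latest of (a) the 1st of the reported month, (b) the first dose date, and (c) the day after the last tumor assessment without progression that precedes the reported progression assessment; it will not be later than the last day of the reported month. The existing minimum with a complete date of death is then applied.

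Three details matter.

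- The floor must be limited to assessments before the reported progression. Protocol 4.3.8.2 keeps scanning subjects treated beyond progression, and an unrestricted floor could push the date past the reported month.
- The order is explicit: floor first, death cap last.
- For duration of CR, the SAP should say that the PET or marrow assessment that dates the CR counts under (c).

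In the three examples the new rule gives 10 March (PFS 1 day), 7 May (DOR 2 days) and 21 March (DOR 2 days). The dates are still early, but the order is possible. The cost is two sentences in the SAP and a small change to date programming, with no new data collection.

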## 9 CONTENT OF REPORTS

All analyses described in the SAP will be included in the Clinical Study Report(s) except where otherwise noted. Refer to the Data Presentation Plan for mock-ups of all tables, figures and listings.

## 10 DOCUMENT HISTORY

**Table 10-1: Document History**

Version Number	Author(s)	Description
1.0	[REDACTED]	Initial version 02-Jun-2014
2.0	[REDACTED]	
01-Sep-2014: updates based on revised protocol 02
 
Section 2.1:
 
 
- Clarification that the 2007 revised IWG criteria is used.
 
- Addition of partial remission rate and duration in the list of secondary endpoints
 
 
Section 3.2: Addition of duration of CR and PR rate and duration
 
Section 3.3: [REDACTED]
 
Section 4.1:
 
 
- Clarification that the 2007 revised IWG criteria is used.
 
- Clarification that for subjects treated beyond progression the BOR is recorded up to the initial progression
 
 
Section 4.2.1: Clarification that the 2007 revised IWG criteria is used.
 
Section 4.2.2: Addition of duration in section title
 
Section 4.2.3: Section added for the PR rate and duration endpoints descriptions
 
Section 4.2.4 : Clarification that the 2007 revised IWG criteria is used.
 
Table 4.2.4-1: clarifications added to the censoring scheme for PFS
 
Section 4.3.2: Clarification that the 2007 revised IWG criteria is used.
 
Section 4.3.7: [REDACTED]
 
Section 4.3.8: [REDACTED]
 
Section 6.3.2: addition of subjects treated beyond progression population
 
Section 7.1: Remove last paragraph about analyses by cohort
 
Section 7.2.1: specify that analyses will be for the 2 cohorts separately and on the pooled population
 
Section 7.2.2: Specify that a summary table will be produced for the 2 cohorts separately and on the pooled population
 
Section 7.3: specify that Analyses from this section will be produced for the 2 cohorts separately and on the pooled population
 
Section 7.3.2:
 
 
- addition of >65 years old category
 
- clarification that the sum of product diameter is used
 
 
Section 7.4: Specify that the analyses will be done for the 2 cohorts separately and pooled
 
Section 7.5: Specify that Unless otherwise specified analyses from this section will be produce by cohort separately
 
Section 7.5.1: Clarification that the 2007 revised IWG criteria is used
 
Section 7.5.2: addition of range of DOR analysis


**Table 10-1: Document History**

Version Number	Author(s)	Description
		
Section 7.5.3: addition of duration of CR in title and range if duration of CR
 
Section 7.5.4: section added to include PR rate and duration analyses
 
Section 7.5.5.1: Clarification that sensitivity for PFS will take into account assessments AFTER subsequent therapy
 
Section 7.5.8: [REDACTED]
 
Section 7.8: [REDACTED]
 
Section 7.8.1: Specify that Unless otherwise specified all analyses from this section will be performed on the two cohorts separately
 
Section 7.8.1.1: [REDACTED]
 
Section 7.8.1.2: [REDACTED]
 
 
- [REDACTED]
 
- Addition of the following analyses based only on pooled ASCT-failed 37 subjects and ASCT ineligible cohorts at IA               
 
- Frequency and percentage BOR based on investigator assessment
 
- ORR based on investigator assessment will be computed along with exact 95% CIs using the Clopper-Pearson method.
 
- OS curves will be estimated using the Kaplan-Meier product limit method. Two-sided, 95% confidence intervals for median OS will be computed.
 
- PFS based on investigator assessment curves will be estimated using the Kaplan-Meier product limit method. Two-sided, 95% confidence intervals for median PFS will be computed.
 
 
 
 
Sections 7.8.2, 7.8.3, 7.8.4: [REDACTED]
 
Section 7.10: Addition of the following tables/figures at IA:           
 
- Spider plot of Tumor Burden Change, per IRRC (on 37 ASCT-failed cohort treated subjects)
 
- Demographic characteristics summary (ASCT Ineligible cohort and pooled with ASCT-Failed 37 subjects)
 
- Best overall response, per investigator (ASCT Ineligible cohort)
 
- [REDACTED]
 
- [REDACTED]
 
- [REDACTED]
 
 

